6.1 PRP vs Minoxidil Study Calendars

Arm A – PRP then MNX

Procedure	Baseline	Week 1	Week 4	Week 5	Week 8	Week 9	Month 3/ Week 12	Month 5/ Week 20	Month 8/ Week 32	Month 12/ Week 48
Consent	X									
Clinical Exam	X						X	X	X	X
Labs	X							X*		X
Phototrichograms & Macroscopic Photos	X						X	X	X	X
Questionnaire	X						X	X	X	X
PRP Injections	X		X		X					
Minoxidil Treatment Daily								X		
Adverse Events		X	X	X	X	X	X	X	X	X
Clinical Assessment of Injection Sites		X		X		X				
Collection of Research Samples	X		X		X					

*- pre-menopausal patients will have a second pregnancy test at the end of the washout period before beginning the cross-over treatment.

Arm B – MNX then PRP

Procedure	Baseline	Month 3/ Week 12	Month 5/ Week 20	Week 21	Week 24	Week 25	Week 28	Week 29	Month 8/ Week 32	Month 12/ Week 48
Consent	X									
Clinical Exam	X	X	X						X	X
Labs	X		X*							X
Phototrichograms & Macroscopic Photos	X	X	X						X	X
PRP Injections			X		X		X			
Minoxidil Treatment Daily	X									
Questionnaire	X	X	X						X	X
Adverse Events		X	X	X	X	X	X	X	X	X
Clinical Assessment of Injection Sites				X		X		X		
Collection of Research Samples			X		X		X			

*- pre-menopausal patients will have a second pregnancy test at the end of the washout period before beginning the cross-over treatment.

7 Statistical Plan

7.1 Sample Size Determination

A total of 23 patients will be enrolled in this study. This sample size will be sufficient in order to gain valuable data to be used in the design of a future, larger study. Given the pilot/feasibility nature of the study, no formal power calculations were performed.

7.2 Statistical Methods

Data Analysis – Given the design, all statistical analysis will be focused on the difference in outcomes, and differences in outcomes compared to baseline, for each treatment within individual patients. For continuous or ordinal outcome variables, we will use a Wilcoxon signed rank test for comparison of outcomes between PRP and Minoxidil, while for categorical outcome variables we will use McNemar's exact test for these. Continuous outcome measures will be summarized using the sample mean, standard deviation, median, minimum, 25th and 75th percentiles, and maximum. Categorical variables will be summarized with number and percentage. 95% confidence intervals (CIs) will be estimated where appropriate. P-values of 0.05 or less will be considered as statistically significant, however the results of these tests will be interpreted with the low power of this pilot study in mind; more emphasis will be placed on graphical and descriptive summaries than on the results of statistical tests. No adjustment for multiple testing will be made owing to the exploratory, pilot nature of the study. Given the prospective nature of the study, we expect to encounter little if any missing data. However in the event of missing data, no attempt to impute this missing data will be made in this pilot study; missing data will be treated as missing.

Descriptive Statistics

We will summarize continuous variables using the sample mean, standard deviation, median, minimum, 25th and 75th percentiles, and maximum. We will summarize categorical variables with number and percentages. Ordinal variables will be summarized using the sample median, minimum, 25th and 75th percentiles, and maximum, as well as with number and percentage.

Handling of Missing Data

Given the prospective nature of the study, we expect to encounter little if any missing data. However in the event of missing data, no attempt to impute this missing data will be made in this pilot study; missing data will be treated as missing.

Multiplicity

No adjustment for multiple testing will be made owing to the exploratory, pilot nature of the study. P-value of 0.05 or less will be considered as statistically significant.

Primary Hypothesis:

We hypothesize that PRP administration for AGA will be safe and without significant complications for the patient. AGA will be comparable in efficacy or superior to conventional treatment with MNX.

The primary endpoints of the study, occurrence of adverse reactions and morbidity, are both dichotomous categorical variables. As such, the proportion for which these outcomes occur will be estimated along with 95% CIs. These proportions will be compared between treatments using McNemar's exact test

Interim Analysis

No interim analysis will be performed in this pilot study.

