CRF	Case Report Form
DSMB	Data and Safety Monitoring Board
FDA	Food and Drug Administration
GCP	Good Clinical Practice
HIPAA	Health Insurance Portability and Accountability Act
IB	Investigator's Brochure
IRB	Institutional Review Board
MNX	Minoxidil
PHI	Protected Health Information
PI	Principal Investigator
PRP	Platelet Rich Plasma
SAE	Serious Adverse Event/Serious Adverse Experience
SOP	Standard Operating Procedure

Study Summary

Title	Minoxidil Foam compared to PRP for Androgenic Alopecia in Women, A Randomized Controlled Pilot Trial
Running Title	PRP for Hair loss in Women
Protocol Number	1
Phase	Pilot
Methodology	Randomized, Controlled, Crossover
Overall Study Duration	12 Months
Subject Participation Duration	12 months
Single or Multi-Site	Single Site
Objectives	Determination of non-inferiority treatment of PRP compared to standard of care MNX in women
Number of Subjects	23
Diagnosis and Main Inclusion Criteria	Female, 18 years or older, Androgenic Alopecia grade I-II by Ludwig classification
Study Product, Dose, Route, Regimen	Platelet Rich Plasma 10cc, Injection by Nappage technique, 3 injections - 1 time every 4 weeks for 3 months
Duration of Administration	12 Weeks (1 time every 4 weeks for 3 months)
Reference therapy	Minoxidil
Statistical Methodology	Wilcoxon signed rank test for comparison of outcomes between treatments and McNemar's exact test for categorical outcome variables

1 Introduction

This document is a protocol for a human research study. This study will be carried out in accordance with the applicable United States government regulations and Mayo Clinic research policies and procedures.

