3.1 General Design

The study will be a randomized control trial following a crossover design to compare PRP to MNX in females.

Subjects will be recruited from the clinical practice of the Department of Dermatology, Mayo Clinic Florida. 23 females with AGA grades I-II based on the Ludwig Classification. (Ludwig)

Patients will be randomized into a PRP then MNX (Arm A) or MNX then PRP group (Arm B). Both treatments will be administered for 12 weeks with a 2 month washout period in between treatments. Hair density and adverse events will be assessed using Phototrichograms, Macroscopic Photos, physical exams and patient questionnaires. All patients will be followed for efficacy and adverse events at 3 month intervals until 1 year after enrollment.

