3.2 Primary Study Endpoints

- 1) Hair growth related to each of the two treatment arms.
- 2) Morbidity related to PRP scalp administration.

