5.5 Prior and Concomitant Therapy

Subjects will not be allowed any concomitant therapy for hair loss treatment.

No prior hair replacement / treatment surgeries.

No topical and systemic therapies for hair loss 3 months prior to study enrollment.

6 Study Procedures

- a.** At baseline all patients will undergo a clinical exam, assessments of hair density using phototrichograms, macroscopic photographs, patient questionnaires and labs including CBC, ferritin, thyroid function, testosterone, TSH and pregnancy test for premenopausal women. All patients will also have a small area shaved at the center of the treatment area, as well as a small tattoo injection to allow for follicle counting via the computerized software.
- b.** At 3 months, 5 months, 8 months and 12 months, patients will have repeat clinical exams and phototrichograms, macroscopic photographs and complete patient questionnaires.
- c.** At 12 months, repeat serum tests (CBC, ferritin, thyroid function, testosterone, TSH) will be performed.
- d.** Adverse events will be assessed at each visit (3, 5, 8 and 12 months post enrollment) as well as 1 week after each injection of PRP.
- e.** Shampoo and conditioner will be standardized with the study supplying Free & Clear brand products to the patients free of charge for the duration of the study.
- f.** Pre-menopausal patients will undergo a second pregnancy test before beginning the cross-over treatment.

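### The PRP–minoxidil hair comparison pools both crossover sequences with no period term, so any shift between month 3 and month 8 widens the confidence interval and costs power

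*Combined protocol and SAP*

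**What the plan says.** The trial is a two-sequence, two-period crossover: Arm A receives PRP then minoxidil, and Arm B the reverse (Sections 3.1 and 5.2). Section 7.1 states that "A total of 23 patients will be enrolled in this study", with no power calculation, to inform a larger study.

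Section 7.2 sets the frame: "all statistical analysis will be focused on the difference in outcomes, and differences in outcomes compared to baseline, for each treatment within individual patients". It then gives the method for continuous and ordinal outcomes: "we will use a Wilcoxon signed rank test for comparison of outcomes between PRP and Minoxidil". It adds that "95% confidence intervals (CIs) will be estimated where appropriate". Nothing in Section 7 mentions period, sequence, or stratification by arm.

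On timing, Section 6 item b states: "At 3 months, 5 months, 8 months and 12 months, patients will have repeat clinical exams and phototrichograms". The calendars in Section 6.1 place the end of the first treatment at month 3, the end of washout at month 5 and the end of the second treatment at month 8. Only the enrolment visit is called baseline. Section 7 names neither the two visits to be paired nor the reference visit for change in the second period.

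Section 3.2 lists as its first primary endpoint "Hair growth related to each of the two treatment arms". The Study Summary gives the objective as "Determination of non-inferiority treatment of PRP compared to standard of care MNX in women".

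**The concern.** The two endpoints being compared lie five months apart, and Section 1.1 describes the condition as progressive. If hair density moves between those visits for reasons unrelated to treatment, Arm A's paired differences are pushed one way and Arm B's the other. A one-sample test on the pooled differences cannot separate this from patient-to-patient noise.

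Two outputs would suffer. One is the between-treatment estimate with its confidence interval, which is what readers will use to judge PRP against minoxidil. The other is the SD of the paired difference, a natural planning input if the larger study is also a crossover. The plan's preference for descriptive summaries over tests does not avoid this, because SDs and confidence intervals are among those summaries.

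**Working it through.** The plan has no power figure to reproduce.

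**Inputs.** From the documents: N = 23; significance at 0.05 (two-sided assumed); hair measured at months 0, 3, 5, 8 and 12. Assumed: arms of 12 and 11 (Section 5.3 gives no ratio); within-sequence SD of the paired difference 1; effect τ = 0.65; normal errors; shift π of 0 to 1 SD.

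**Where the shift goes.** Let D = PRP − minoxidil, and let π be the change from month 3 to month 8 that both arms share.

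- Arm A: mean of D = τ − π
- Arm B: mean of D = τ + π

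**Pooled SD.** SD = √(1 + 4π²·nA·nB/[N(N−1)]). At 12/11 the multiplier is 4·12·11/(23·22) = 528/506 = 1.04, so the SD and CI widen by about √(1 + (π/SD)²). For π = 0, 0.25, 0.5 and 1.0 the pooled SD is 1.00, 1.03, 1.12 and 1.43.

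**Bias of the pooled mean.** π(nB − nA)/N = −π/23, or about 0.04π in size at 12/11. At an assumed 13/10 it is 3π/23 = 0.13π.

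**Period-adjusted estimate.** Month 3 minus month 8 has mean τ − π in Arm A and −τ − π in Arm B. Their difference is 2τ, so π cancels and half the difference estimates τ.

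**Simulation at 12/11** (at least 20,000 trials per setting):

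| Shift (SD) | 0 | 0.25 | 0.5 | 1.0 |
|---|---|---|---|---|
| Power, pooled signed rank | 82% | 80% | 72% | 42% |
| Power, rank-sum by sequence | 80–81% | 80–81% | 80–81% | 80–81% |
| Power, period-adjusted t | 84% | 84% | 84% | 84% |
| CI half-width, pooled | 0.43 | 0.44 | 0.48 | 0.61 |
| CI half-width, adjusted | 0.43 | 0.43 | 0.43 | 0.43 |
| Coverage, pooled CI | 95% | 96% | 97% | 99% |
| Type I error, pooled signed rank | 5% | 4% | 3% | 0.6% |

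The loss due to the shift is best read along the signed-rank row: about 2, 10 and 40 points.

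**Which outcome scale is exposed.** Suppose drift is constant at g per month.

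- Raw values, month 3 against month 8: 8g − 3g = 5g
- Change from enrolment: (8g − 0) − (3g − 0) = 5g; the enrolment value cancels from D, so this scale gives no protection
- Period-2 change from month 5: (8g − 5g) − (3g − 0) = 0

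**Effect on planning.** Pooled SDs of 1.12 and 1.43 correspond to variances of 1.26 and 2.04. A sample size based on that variance would be about 26% or 104% too large.

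**The case against.** **The harm rests on an assumed shift.** This stands. The documents give a direction at most, never a size. Below 0.25 SD the loss is minor, and the 42% figure needs a full 1.0 SD.

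**Section 7.2 can be read as giving each treatment its own baseline.** If period-2 change runs from month 5, constant-rate drift cancels. That reading is open, but the plan does not state it, and the only visit it calls baseline is enrolment. Raw outcomes are also to be compared, and they remain exposed on either reading.

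**This is a pilot with descriptive emphasis, and hair growth may not be the analytic primary.** This stands in part. Section 7.2 names only adverse reactions and morbidity as primary endpoints, analysed by McNemar's test, which conflicts with Section 3.2. No non-inferiority margin is stated, so no decision rule depends on the CI width. Sequence is recorded, so the analysis could be redone later, but choosing the adjusted version after seeing the data would be post hoc.

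**Stronger readings that a reader might infer.** One is that the planned test risks false positives or a materially biased estimate. It does not: its type I error falls as the shift grows, and bias is about 0.04 of the shift at 12/11. Another is that skewed data make one of these tests invalid. With skewed period differences and no treatment effect, all three reject at about 5%. A third is that adjusting for period deals with carryover. It does not. If PRP leaves residuals r5 at month 5 and r8 at month 8 in Arm A only, the month 3/8 estimate is biased by −r8/2, and month-5 change scores by (r5 − r8)/2. Neither choice is better in every case.

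**Conclusion.** The point holds as a moderate, inexpensive improvement. The planned comparison ignores period in a crossover and does not say which baseline applies in the second period. On raw outcomes or change from enrolment, a month-3 to month-8 shift inflates the pooled SD and CI by about √(1 + (π/SD)²): 3% at 0.25 SD, 12% at 0.5 SD and 43% at 1.0 SD. The test becomes conservative to match.

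These sizes rest on an assumed effect of 0.65 SD, normal errors and a 12/11 split; the true shift is unknown and could be negligible. The documents do not support a claim that the hair-growth result would be misleading in direction, or that a non-inferiority conclusion would fail.

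**What to change.** In Section 7.2:

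1. Name months 3 and 8 as the paired visits for the PRP–minoxidil hair comparison.
2. Make the main analysis period-adjusted: a linear model with treatment, period **and a patient effect**. Equivalently, compare month 3 minus month 8 between Arm A and Arm B with a two-sample t-test, and **halve** the difference and its CI to obtain the PRP − minoxidil effect.
3. For ordinal or clearly non-normal outcomes, use the rank-sum test by sequence, with the Hodges–Lehmann estimate and CI also halved.
4. Report results by sequence, and the SD of paired differences pooled within sequence.
5. Keep change from month 5 as a sensitivity analysis, and show month 5 against enrolment by arm descriptively.
6. State that a period term does not remove carryover.

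The patient effect is essential. With treatment and period alone the pairing is lost: with no shift and an assumed within-patient correlation of 0.5, 0.8 or 0.9, power falls to about 60, 11 or 1%, and the CI half-width rises to about 0.59, 0.94 or 1.33.

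The cost is wording only, with no new visits or data. If there is no shift, the rank version gives up about 2 points of power and the linear version essentially none.

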3.4 Primary Safety Endpoints

- 1) Documentation will include levels of pain at injection sites, any evidence of adverse reaction in the skin (e.g., swelling, erythema, warmth) and any other concerns expressed by patients.

4 Subject Selection Enrollment and Withdrawal

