8.2 Recording of Adverse Events

All adverse events will be documented as required under 21 CFR part 1271. Depending on the nature and seriousness of the adverse reaction, the IRB will be notified according to the Mayo Clinic IRB policy. If An SAE occurs it will also be reported to the FDA as per regulations

At each contact with the subject, the study team must seek information on adverse events by specific questioning and, as appropriate, by examination. Information on all adverse events should be recorded immediately in the source document, and also in the appropriate adverse event section of the case report form (CRF) or separate worksheet. All clearly related signs, symptoms, and abnormal diagnostic, laboratory or procedure results should recorded in the source document.

All adverse events occurring during the study period must be recorded. The clinical course of each event should be followed until resolution, stabilization, or until it has been ultimately determined that the study treatment or participation is not the probable cause. Serious adverse events that are still ongoing at the end of the study period must be followed up, to determine the final outcome.

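### Sections 3.2 and 7.2 conflict on the morbidity endpoint: tied to PRP, the planned McNemar test does not compare treatments; untied, morbidity is undefined

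*Combined protocol and SAP*

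**What the plan says.** Section 3.2 (Primary Study Endpoints) has two entries: hair growth in each arm, and "Morbidity related to PRP scalp administration". Section 7.2 (Statistical Methods) describes the primary endpoints differently: "occurrence of adverse reactions and morbidity, are both dichotomous categorical variables". Hair growth is not in that sentence, adverse reactions are added, and morbidity is no longer tied to PRP. Each proportion is to be estimated with a 95% CI, and then "These proportions will be compared between treatments using" McNemar's exact test.

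No section says what counts as morbidity. Section 3.4 (Primary Safety Endpoints) lists what is to be documented: pain at injection sites, "any evidence of adverse reaction in the skin (e.g., swelling, erythema, warmth"), and other concerns that patients raise. It does not say which of these is morbidity and which is an adverse reaction.

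On ascertainment, Section 6, item d, covers study visits and PRP injections: "Adverse events will be assessed at each visit (3, 5, 8 and 12 months post enrollment) as well as 1 week after each injection". Section 8.2 adds "At each contact with the subject, the study team must seek information on adverse events by specific questioning". The Section 6.1 calendars show more adverse-event contacts during a PRP course than during an MNX course. Both courses end with the same assessment: under Section 6, item b, "patients will have repeat clinical exams and phototrichograms, macroscopic photographs and complete patient questionnaires" at months 3, 5, 8 and 12.

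**The concern.** McNemar's test compares patients who have the event only on PRP with patients who have it only on MNX. If the event is defined as caused by PRP administration, the second group is empty by definition. A p-value at or below 0.05 could then be reported as a difference between PRP and MNX although nothing observed on MNX could have changed it. If the unqualified wording of Section 7.2 is intended, the analyst has no rule for scoring morbidity in either period, and none for separating it from the other primary safety endpoint.

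The stake is a primary safety endpoint in a pilot whose stated purpose (Section 7.1) is to supply data for designing a larger study. The plan's caveat about low power would not alert a reader, because low power is a different problem.

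A smaller matter affects the adverse-reaction comparison. Events are sought more often on PRP than on MNX, and the plan does not list this as a limitation.

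**Working it through.** The plan gives no event rate or power figure to reproduce. Section 7.1 sets 23 patients without a power calculation.

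**Inputs.** At most 23 pairs (Section 7.1); significance at p of 0.05 or less (Section 7.2); contact weeks from Section 6.1. Sidedness is not stated, so I assume two-sided tests.

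**1. McNemar's test on the Section 3.2 wording.** Let b be the number of patients with the event on PRP only and c the number with it on MNX only. The exact two-sided p-value is min(1, 2 × P[X ≥ max(b, c)]), with X binomial on b + c trials and probability 0.5. Under Section 3.2, c = 0 by construction and every patient with PRP morbidity is a PRP-only pair, so

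p = min(1, 2 × 0.5^b).

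- b = 5: 2 × 0.03125 = 0.0625
- b = 6: 2 × 0.015625 = 0.03125

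The test rejects exactly when 6 or more patients have PRP morbidity. It is a threshold on the PRP count. The number of complete pairs and the MNX experience do not enter.

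**2. What the test would do if MNX could score.** Keep b = 6 and vary c:

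| PRP only | MNX only | p |
|---|---|---|
| 6 | 0 | 0.031 |
| 6 | 1 | 0.125 |
| 6 | 2 | 0.289 |
| 6 | 6 | 1.0 |

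The same six PRP patients lead to very different conclusions according to the MNX count. The Section 3.2 wording removes that information.

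**3. What the PRP data can show alone.** Clopper-Pearson 95% intervals for x of 23:

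- 0/23: upper limit 1 − 0.025^(1/23) = 14.8%, so 0% to 14.8%
- 6/23: 10.2% to 48.4%

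**4. On-treatment adverse-event contacts.**

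| Source | PRP course | MNX course |
|---|---|---|
| Calendar, Arm A | weeks 1, 4, 5, 8, 9, 12 = 6 | week 32 = 1 |
| Calendar, Arm B | weeks 21, 24, 25, 28, 29, 32 = 6 | week 12 = 1 |
| Section 6, item d, alone | 3 post-injection + 1 end-of-course = 4 | 1 |

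These counts leave out the day a course starts and the visits after it ends. Adding the next off-treatment visit to the calendar counts gives 7 vs 2. The direction is the same on every count.

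**The case against.** The strongest reply is that Section 7.2 is endpoint wording too, and it carries no PRP qualifier. It does not simply restate Section 3.2, since it drops hair growth and adds adverse reactions. It compares proportions between treatments, in a section that analyses outcomes for each treatment within patients. The natural reading there is morbidity counted in each period, with no structural zero. This stands. A reader might infer that the McNemar test is empty under any reading; the documents do not support that. What they establish is a conflict between two sections, with an empty comparison on one wording and an undefined endpoint on the other. The missing definition affects PRP as much as MNX.

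A reader might also infer a large excess of false findings against PRP by setting rejection probabilities under the Section 3.2 wording beside those for two treatments of equal risk. That comparison changes two things at once, the wording and the true MNX rate. With 23 complete pairs and assumed PRP morbidity of 10%, 20%, 30% and 40%, the Section 3.2 wording rejects with probability 2.3%, 30.5%, 73.1% and 94.6%. If MNX can score at an assumed 2%, in independent periods, the figures are 1.5%, 22%, 60% and 87%; at 5% they are 0.8%, 14%, 44% and 74%. When MNX morbidity is rare, the wording alone makes a more modest difference. The documents give no event rates, so I claim no such excess.

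On contacts, extra visits after injections are ordinary safety follow-up. Section 3.1 says "Hair density and adverse events will be assessed using Phototrichograms, Macroscopic Photos, physical exams and patient questionnaires", and both courses end with the same set of assessments, so MNX reactions still present then can be seen without relying on recall. A reader might infer that 6 vs 1 proves bias against PRP. It does not: any bias depends on how well transient MNX events are recalled, which is unknown.

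Finally, the safety hypothesis in Section 7.2 concerns PRP alone, and the proportion with its CI, already planned, addresses it.

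**Conclusion.** The concern holds as a conflict between Sections 3.2 and 7.2 that should be resolved before analysis. On the Section 3.2 wording, the morbidity test is not a between-treatment comparison: significance is reached at 6 patients with PRP morbidity and missed at 5, regardless of MNX. This rests only on a two-sided exact test. On the Section 7.2 wording, the test could be valid, but the endpoint needs a definition first.

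The consequence is limited. Section 7.2 places description above tests, no decision in the plan depends on the p-value, and the estimate that answers the PRP safety question is already planned.

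The unequal contacts (6 vs 1 by the calendars, 4 vs 1 by Section 6, item d) are a limitation to state, with bias of unknown size. They do not invalidate the adverse-reaction comparison.

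**What to change.** Reconcile Sections 3.2 and 7.2 in one of two ways.

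1. **Keep morbidity PRP-specific.** In Section 7.2, restore the qualifier, delete the McNemar test for morbidity, and report the PRP proportion with a Clopper-Pearson 95% CI. Cost: the between-treatment morbidity p-value is lost.
2. **Compare treatments.** Amend both Section 3.2 and Section 7.2 to define morbidity so that it can be scored on either treatment, for example from the skin-reaction items in Section 3.4, and keep McNemar's test. Cost: a second section changes, injection-site pain would be outside a definition built on those items, and the endpoint would overlap with adverse reactions and share the contact limitation.

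In either case, keep the adverse-reaction comparison on all contacts and add a sentence that on-treatment contacts are unequal and the resulting bias cannot be sized. A descriptive table of events at the common end-of-course visits (months 3 and 8) is optional. It has an opposite bias: Section 1.4 expects local PRP reactions to last 2 to 3 days, the last injection is 4 weeks before that visit (week 8 to 12, or 28 to 32), and MNX is applied daily through its course.

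The change is wording only, submitted to the IRB as an amendment (Section 11). It needs no added visits or forms.
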